### 6.3.3 Exploratory Analysis

Overall survival (OS) will be analyzed in efficacy population. OS is defined as the time from the date of first dose until the date of death from any cause. This is the length of time from the start of treatment that patients are still alive. Subjects alive at the end of the study or lost to follow-up will be censored on the date of last follow-up disease assessment.

Disease-free survival (DFS) will be analyzed in primary efficacy population. DFS is defined as the time from the first date of no disease (i.e., date of surgery with complete resection) to local or distant recurrence or death due to any cause, whichever occurs first. DFS will be analyzed only for patients who underwent surgery with complete resection. After surgery with complete resection, data for patients who withdraw from the study without disease recurrence or death will be censored at the date of last disease follow-up assessment. Patients without post-surgery disease follow-up assessments but known to be alive will be censored at the date of surgery with complete resection plus one day.

Event-free survival (EFS) will be analyzed in efficacy population. EFS is defined as the time from the date of first dose to any of the following events, whichever occurs first:

- Progression of disease per RECIST v1.1 that precludes surgery with complete resection
- Local or distant disease recurrence
- Death due to any cause

Patients who have not experienced disease progression that precludes surgery with complete resection, local or distant disease recurrence, or death at the time of analysis will be censored at the time of last tumor or disease follow-up assessment. Patients with no post-baseline tumor or disease follow-up assessment but known to be alive will be censored at the date of first dose plus one day.

The durations of overall survival, disease-free survival and event-free survival will be computed in months as:

$$\frac{(End\ Date - Start\ Date + 1)}{(365.25/12)}$$

The overall survival, disease-free survival and event-free survival will be analyzed using the Kaplan-Meier method for the efficacy population. To describe overall survival, the survival rate, death rate, and overall median, 95% CI, 25th and 75th percentiles, and range will be reported. Furthermore, the patients remaining alive, survival rate, and 95% CI will be reported every 6 months (at 6, 12, 18, 24, 30, and 36 months). To describe disease-free survival and event-free survival, the disease-free rate, not disease-free rate, counts of patients by contributing events, and overall median, 95% CI, 25th and 75th percentiles, and range will be reported. Furthermore, the patients remaining disease-free, disease-free rate, and 95% CI will be reported every 6 months (at 6, 12, 18, 24, 30, and 36 months).

These analyses will also be repeated for each subgroup of major pathologic responder and non-responder, and by subgroups of PD-L1 negative (TC0IC0) and positive (TC123IC123). Subgroups will be compared using a log-rank test.

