3.1.3 Surveillance

All patients who undergo surgery will enter the Surveillance Period. During Surveillance, patients will be monitored by extended chest CT scans (including liver and adrenals). Whole blood will be collected for plasma and serum, and PBMCs (at selected timepoints), every 6 weeks to 3 months for 2 years for correlative studies (see [Appendix 2](#) for details). Upon completion of Surveillance, patients enter Survival Follow-up. Patients whose disease progresses or recurs during Surveillance will discontinue from Surveillance and enter Survival Follow-up.

For patients previously enrolled under Protocol Version 3 or earlier:

- If the patient re-consents under Protocol Version 4 >3 months after the Post-surgery Visit: patient will not enter Surveillance and will follow the schedule of activities from Protocol Version 3 (see [Appendix 11](#)).
- If the patient re-consents under Protocol Version 4 at any time between Screening and the Post-surgery Visit: patient will be offered to enter Surveillance and follow Protocol Version 4 schedule of activities.
- If the patient re-consents under Protocol Version 4 ≤ 3 months after the Post-surgery Visit: patient will be offered to enter Surveillance and follow Protocol Version 4 schedule of activities only if post-surgery baseline chest CT scan is available. If chest CT scan is not available, patient will follow the schedule of activities from Protocol Version 3 (see [Appendix 11](#)).

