Approximately 180 patients with histologically documented Stage IB, II, IIIA, and selected IIIB NSCLC and are eligible for surgical resection with curative intent will be enrolled in the Neoadjuvant Atezolizumab Therapy Phase of this study. Approximately 50 patients who complete neoadjuvant atezolizumab therapy are expected to continue on to the Adjuvant Atezolizumab Therapy Phase.

4.1.1 **Inclusion Criteria**

Neoadjuvant Atezolizumab Therapy

Patients must meet the following criteria for study entry:

- Signed Informed Consent Form
- Age \geq 18 years
- Able to comply with the study protocol, in the investigator's judgment
- Pathologically documented NSCLC
 - Stage IB, II, IIIA, or selected IIIB, including T3N2 or T4 (by size criteria, not by mediastinal invasion) NSCLC (based on the 8th edition of the American Joint Committee on Cancer [AJCC] Non-Small Cell Lung Cancer Staging system; see [Appendix 4](#)). Note: Patients may be enrolled based on clinical stage, but documentation of nodal involvement by endobronchial ultrasound (EBUS) or mediastinoscopy for patients with clinical Stage II and IIIA disease is encouraged.
- Measurable disease, as defined by RECIST v1.1
- NSCLC must have a solid or subsolid appearance on CT scan and cannot have a purely ground glass opacity (GGO) appearance. For subsolid lesions, the tumor size (i.e., clinical T stage) should be measured based on the solid component only, exclusive of the GGO component
- Evaluated by the operating attending surgeon prior to study enrollment to verify that the primary tumor and any involved lymph nodes are technically completely resectable
- Adequate pulmonary function to be eligible for surgical resection with curative intent
 - Pulmonary function tests (PFTs) must have been performed within 6 months of planned resection and repeated at screening and should include lung volumes, spirometry, and a diffusion capacity. Abnormal PFTs may be further evaluated with quantitative ventilation/perfusion scanning or cardiopulmonary exercise testing. Postoperative percent predicted forced expiratory volume in 1 second (FEV1) and diffusion capacity must be $\geq 40\%$ and/or maximal oxygen consumption (VO_2 max) should be > 10 mL/kg/min.

- Adequate cardiac function to be eligible for surgical resection with curative intent
 - If clinically indicated, patients with underlying ischemic or valvular heart disease should be evaluated preoperatively by a cardiologist.

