4.5.6 Tumor and Response Evaluations

Neoadjuvant Atezolizumab Therapy Phase

During the Neoadjuvant Atezolizumab Therapy Phase, the patient's tumor will be staged at screening by contrast-enhanced (if patient is not contrast-allergic) helical CT scan of the chest, PET-CT, and brain MRI, preferably with gadolinium (for Stage II or IIIA disease). If brain MRI is not feasible for technical or patient-related reasons (e.g., pacemaker, severe claustrophobia), brain CT scan with IV contrast should be obtained. All scans will be repeated prior to surgery to confirm surgical eligibility.

At the investigator's discretion, scans may be repeated at any time if progressive disease is suspected.

Radiographic responses will be assessed by the investigator per RECIST v1.1 after two cycles of neoadjuvant atezolizumab.

Pathologic responses will be assessed from surgically resected tumor by the site pathologist.

All radiologic digital imaging (including CT and CT/PET scans plus all supporting radiologic interpretation or reports) will be submitted for central review. The timepoints are:

- Time of biopsy
- Pre-surgery
- Post-surgery
- Or at any time of disease progression

Surveillance

For all patients who enter surveillance, extended Chest CT scans (including liver and adrenals) will be performed approximately every 6 weeks to 3 months for up to 2 years (see [Appendix 2](#)); all other non-protocol specified tumor assessments will be performed per standard clinical practice.

For patients that receive any adjuvant treatment (Subgroups B, C, and D): In order to align adjuvant treatment with Surveillance assessments, timing of the initial post-baseline extended chest CT scan and blood draws will be flexible (see [Appendix 2](#)). For patients in Subgroup D: Extended Chest CT Scan and blood drawn are required at C1D1 (± 5 days) of adjuvant atezolizumab phase. If C1D1 falls in between surveillance visits, an extra extended Chest CT scan needs to be done and subsequent surveillance visits will be adjusted accordingly (at every 3 months after adjuvant atezolizumab C1D1).

All radiologic digital imaging (including CT and CT/PET scans plus all supporting radiologic interpretation or reports) will be submitted for central review. The timepoints are:

- Post-surgery (or new baseline)
- Surveillance timepoints
- Or at any time of disease progression

Adjuvant Atezolizumab Therapy Phase

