6.4.3 Exploratory Efficacy Endpoints

Changes in tumor and immune markers from baseline to surgery will be assessed in tissue samples. Also, changes in the circulating immuno-phenotype will be assessed.

DFS is defined as the time from the first date of no disease (i.e., date of surgery) to local or distant recurrence or death due to any cause, whichever occurs first. DFS will be analyzed only for patients who underwent surgery. After surgery, data for patients who withdraw from the study without documented disease recurrence or death and for whom there is evidence in the eCRF that disease follow-up evaluations were performed will be censored at the date of the last assessment when the patient is known to be free from disease recurrence (that is, last scan or collection of recurrence information when the patient is known to be free from disease recurrence). Patients without post-surgery assessments but known to be alive will be censored at the date of surgery plus one day.

Time to event analyses of OS and DFS will be calculated using the Kaplan-Meier method for all patients in the efficacy population and for subgroups of responders and non-responders and PDL-1 negative and positive.

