### 3. STUDY DESIGN

#### 3.1 Overview of Study Design

This is a Phase II, open-label, single-arm study, designed to evaluate the efficacy of atezolizumab as a neoadjuvant therapy in patients with Stage IB, II, IIIA, or selected IIIB NSCLC scheduled for curative-intent resection by evaluating response to treatment. In addition, the safety of atezolizumab will be evaluated in this treatment setting. The study is also designed to investigate a number of laboratory correlative studies to further define the mechanism of anti-tumor activity of atezolizumab and several potential predictive biomarkers, which will help identify patients who are more likely to respond to treatment, and to aid in the design of future clinical trials. A

strong correlation between PD-L1 expression and response to the anti -PD-1/PD-L1 antibodies has been demonstrated (Brahmer et al. 2010; Garon et al. 2015; Vansteenkiste et al. 2015), indicating that PD-L1 is potentially useful as a predictive biomarker. Finally, the study will also include DFS, EFS and OS as exploratory endpoints.

Approximately 180 patients with NSCLC will be enrolled in this study at approximately 15 study centers in the United States. The study will be conducted in two parts, a Neoadjuvant Atezolizumab Therapy Phase and an Adjuvant Atezolizumab Therapy Phase. During the Neoadjuvant Atezolizumab Therapy Phase, approximately 180 patients with pathologically documented Stage IB, II, IIIA, and selected IIIB NSCLC and who are eligible for surgical resection with curative intent will be enrolled to receive two doses of atezolizumab as neoadjuvant therapy. Primary and secondary efficacy analyses, safety analyses, and exploratory biomarker analyses will be conducted on this cohort.

All patients who undergo surgery will enter a Surveillance period and will be monitored for disease recurrence using extended chest CT and serial blood samples for biomarker assessments for up to 2 years after surgery. Patients who do not undergo surgery will move directly to Survival Follow-up.

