Patients will be closely monitored for safety and tolerability throughout the study. Safety assessments will include collection and monitoring of adverse events and laboratory abnormalities graded per the National Cancer Institute Common Terminology Criteria for Adverse Events, Version 4.0 (NCI CTCAE v4.0). Laboratory safety assessments will include the regular monitoring of hematology and blood chemistry. Tumor tissue samples, normal lung parenchyma, whole blood samples, and optional lymph node samples will be collected for biomarker assessments.

After Surveillance completion, patients will enter the Survival Follow-up period and will be followed per SOC, but information on off-protocol cancer-treatment, recurrence and survival will be collected every 6 months for up to 3 years after the patient receives the last dose of atezolizumab on study. Patients who discontinue the study due to adverse events will be followed until resolution or stabilization of the adverse event.

[figure not shown]
The Neoadjuvant Atezolizumab Therapy Phase will end when the last data point required for primary efficacy analysis (i.e., pathology evaluation at time of surgery) is obtained. This is expected to occur approximately 30 days after the last patient's surgery.

The Surveillance period will end 2 years after the post-surgery visit. After completing neoadjuvant or adjuvant treatment with atezolizumab, patients will be followed for survival for up to 3 years. For patients that undergo surgery and enter Surveillance, time in Surveillance will overlap with time in Survival Follow-up.

The total length of the study, from screening of the first patient to the end of the study, is expected to be approximately 6 years.

The study schema is illustrated in Figure 1, and a schedule of assessments is presented in Section 4 of this statistical analysis plan.

**Figure 1** Study Schema

CT=computed tomography; MRI=magnetic resonance imaging; PET= positron emission tomography; PFT = pulmonary function test; SOC = standard of care.

a Refer to Appendix 2 in the protocol , Timing of Surveillance Assessments.

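### Overall survival is censored at an undefined last disease assessment instead of the last date known alive, so late OS estimates can be biased downward

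*SAP*

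**What the plan says.** SAP 6.3.3 measures OS from first dose to death from any cause and gives one censoring rule: "Subjects alive at the end of the study or lost to follow-up will be censored on the date of last follow-up disease assessment". It asks for Kaplan-Meier OS at 6, 12, 18, 24, 30 and 36 months, repeated by major pathologic response (MPR) and by PD-L1 group with log-rank tests. Protocol 6.4.3 plans the OS analysis but gives no OS censoring rule.

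The term in the OS rule is not defined. Two nearby passages bear on it:

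- The SAP's rule for event-free survival (EFS) treats being alive and having an assessment as different things: "Patients with no post-baseline tumor or disease follow-up assessment but known to be alive will be censored" one day after first dose.
- Protocol 6.4.3 describes the disease-free survival (DFS) censoring date as the "last scan or collection of recurrence information when the patient is known to be free from disease recurrence".

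The follow-up schedule is as follows:

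- Surveillance imaging ends 2 years after the post-surgery visit, and earlier at recurrence: "Patients whose disease progresses or recurs during Surveillance will discontinue from Surveillance and enter Survival Follow-up" (Protocol 3.1.3).
- For unoperated patients, "Patients who do not undergo surgery will move directly to Survival Follow-up" (SAP 3.1). Their last scheduled scan is the pre-surgery one: "All scans will be repeated prior to surgery to confirm surgical eligibility" (Protocol 4.5.6).
- After that, "information on off-protocol cancer-treatment, recurrence and survival will be collected every 6 months for up to 3 years" following the last dose (SAP 3.1). Protocol 4.5.6 allows clinic visit, telephone, mail or email.
- Protocol 4.6.1 allows survival status to be taken from public records after withdrawal.

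**The concern.** The usual OS censoring date is the last date the patient was known to be alive. The SAP uses a disease-assessment date, and in this trial the two can be far apart: after recurrence, after the end of imaging, and for patients who never had surgery.

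In that gap the rule treats the living and the dead differently. If a contact or record shows a death, the death enters at its true date. If it shows the patient alive, the OS time may still stop at the earlier assessment. Censoring then depends on survival itself, which breaks the Kaplan-Meier assumption of non-informative censoring.

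At stake are the 30- and 36-month OS estimates, the reported median, and the OS comparisons by MPR and PD-L1 group, because those groups may differ in recurrence, surgery and length of follow-up.

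**Working it through.** The documents state no OS rate, event count or OS power, so there is no plan figure to reproduce. The check has four steps.

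**1. Timeline, from the documents.** Protocol Appendix 1 places surgery at day 40 (±10) and the post-surgery visit 4 to 6 weeks later. In Appendix 2, S1 and S2 follow at 6-week steps and S3 to S9 at 3-month steps. One month is 365.25/12 = 30.44 days (SAP 6.3.3).

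- Post-surgery visit: (40 + 35)/30.44 = 2.46 months from first dose.
- S9: 84/30.44 + 7 × 3 = 23.76 months after that visit, which agrees with the stated 2 years.
- Last scheduled scan: 2.46 + 23.76 = 26.2 months from first dose. With surgery and visit at the window limits (58 or 92 days) the range is 25.7 to 26.8.
- End of survival follow-up without adjuvant atezolizumab: 21/30.44 + 36 = 36.7 months.

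For those patients the 30- and 36-month estimates lie after the last scheduled scan and rest on survival contacts. Patients on adjuvant atezolizumab are followed 3 years from a later last dose, but their scans also stop at 2 years of Surveillance.

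**2. Direction, without assumed rates.** The estimate is S(t) = ∏(1 − dⱼ/nⱼ) over death times up to t. Censoring living patients earlier leaves every dⱼ unchanged and can only reduce nⱼ. Each factor stays the same or falls, and so does S(t).

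**3. Size, by simulation.** Three readings of the rule were compared with censoring at last date known alive:

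- A: only scheduled scans count.
- B: scans and recurrence contacts count until recurrence.
- C: every survival contact counts.

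Assumptions (not in the documents): n = 165; 24-month recurrence 20/30/40%; monthly death hazard 0.0008/0.0015/0.0025 without recurrence and 0.02/0.03/0.04 after it (the latter also for unoperated patients); 5% or 12% unoperated; adjuvant start 1.5 to 6 months after surgery, for 6 to 12 months. The adjuvant share of 50/180 is the protocol's expectation (Section 4.1). Follow-up is 36 months after the last dose.

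| | Last known alive | A | B | C |
|---|---|---|---|---|
| 36-month OS, range | 0.63 to 0.88 | 0.20 to 0.28 | – | as last known alive |
| Shortfall at 36 months, points | – | 43 to 60 | 1.6 to 5.4 | 0 |
| Shortfall at 30 months, points | – | 18 to 23 | 1.0 to 3.6 | 0 |
| Shortfall through 24 months, points | – | 0.6 to 2.2 | 0.6 to 2.2 | 0 |
| 36-month OS, middle rates, 5% unoperated | 0.776 | 0.256 | 0.745 | 0.776 |

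In the last row the shortfall is 77.6 − 25.6 = 52.0 points under A and 77.6 − 74.5 = 3.1 under B. Under A, 8 to 18 patients are at risk at month 30 instead of 114 to 149. The median then appears to be reached at about 31 to 33 months in at least 97% of runs, although it is not reached with last-known-alive censoring. The shortfall under A is 35 to 50 points with 50% on adjuvant treatment and 58 to 80 with none.

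A second set of assumed rates (10/12/15% unoperated, no adjuvant extension, 400,000 patients per scenario) gives 36-month OS of 82.2/73.2/62.1% with last known alive, 5.6/5.0/4.4% under A and 80.2/69.4/56.5% under B. Reading B is therefore 2.0/3.8/5.6 points low, and reading C is unbiased.

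**4. Subgroups.** Assume 20% MPR and a recurrence hazard ratio of 0.5. The 36-month OS difference between MPR groups, for the three sets of rates, is then 4.1/7.4/10.3 points with last known alive, 4.8/9.2/13.0 under B and 23.3/11.9/8.0 under A. Now assume equal true survival, with adjuvant atezolizumab in 60% of MPR patients and 22% of others. Reading A then shows a false difference of 14 to 20 points, and B shows none.

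**The case against.** The strongest reply is that reading C is what the trial would do in practice. The 6-monthly contact collects treatment, recurrence and survival together, for unoperated patients as well (Protocol Appendix 1), and its output is a single listing, Survival and Recurrence Follow-up (Listing 16.2.6.14). The EFS rule names tumor assessment separately from disease follow-up assessment, and the protocol's DFS wording accepts recurrence information without a scan. Both count against scans only. The recurrence-free condition in reading B belongs to DFS and is not in the OS sentence. Even under B the shortfall is of the order of sampling error or below: at n = 165 and OS 0.776 the 95% half-width is 1.96 × √(0.776 × 0.224/165) = 6.4 points.

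Much of this stands. Reading A is the least likely of the three, so its figures show how wide the ambiguity is and do not forecast the result. The sizes rest on assumed rates, and no data cut-off was modelled, although SAP Section 7 also schedules the OS tables for the interim efficacy and primary analyses.

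It does not remove the problem. No passage says that every contact counts. The SAP itself separates being known alive from having an assessment, and the nearest definition stops at recurrence. A public-record check is not a disease assessment on any reading. Unlike DFS and EFS, OS has no rule for a living patient without a post-baseline assessment. A systematic downward shift is also not excused by being smaller than the confidence interval.

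**Conclusion.** The concern holds. The OS rule uses the wrong kind of date and an undefined term. The downward direction follows from the Kaplan-Meier formula and needs no assumed rates. The bias is absent only if every contact or record showing the patient alive counts as a disease assessment, and the documents do not say so.

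The size is conditional on the reading and on the assumed recurrence and death rates and unoperated share. At 36 months it runs from nil (every contact) through 1.6 to 5.4 points (contacts until recurrence) to 43 to 60 points (scans only, 50/180 on adjuvant treatment). Through 24 months it is about 2 points or less. Comparisons by MPR and PD-L1 group use the same OS times and can be distorted too. OS is exploratory and the primary MPR analysis is unaffected, so this should be fixed but does not threaten the trial's main conclusion.

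**What to change.** Replace the OS censoring sentence in SAP 6.3.3 with:

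> Patients not known to have died by the data cut-off will be censored at the last date known alive from any source (visit, survival contact, public record); patients with no post-baseline information will be censored at first dose plus one day.

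Keep censoring at the last disease assessment for DFS and EFS, and define that term there, stating whether a recurrence contact without a scan counts.

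The cost is one SAP sentence for OS, plus the definition for DFS and EFS. The survival contact dates are already collected and appear in Listing 16.2.6.14, so no new data are needed.

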## 5. ANALYSIS POPULATIONS

Data will be summarized using the following analysis populations.

- All Enrolled Subjects: This analysis population will include all enrolled subjects, regardless of whether they received any amount of study drug. The all enrolled subjects population will be used for the summarization of subject disposition.
- Safety Population: This analysis population will include all enrolled subjects who have received any dose of study drug. The safety population will be used for the analysis of safety measures.
- Efficacy Population: This analysis population will include all enrolled patients who have received at least one dose of the study drug and who do not have EGFR or ALK mutant tumors.
- Primary Efficacy Population: This analysis population will include all efficacy population subjects, excluding patients who have not received surgery after neoadjuvant treatment with Atezolizumab, and excluding subjects who have not had a complete resection. This population will be used for primary efficacy analysis. For the primary efficacy population, if major pathological response is unable to be assessed, then it will remain undetermined and the subject will be removed from this population.

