	Table 14.1.10.2	Study Drug Exposure, Surveillance/Survival Follow-up Phase	Safety Population
S, P	Table 14.1.11.1	Prior Medications	Safety Population
S, P	Table 14.1.11.2	Concomitant Medications, Neoadjuvant Atezolizumab Therapy Phase	Safety Population
	Table 14.1.11.3	Concomitant Medications, Surveillance/Survival Follow-up Phase	Safety Population
E, P	Table 14.2.1	Primary Efficacy Analysis for Major Pathologic Response Rate	Primary Efficacy Population
E, P	Table 14.2.2.1	Major Pathologic Response Rate within PD-L1 Group	Efficacy Population
E, P	Table 14.2.2.2	Investigator-assessed Response Rate within PD-L1 Group	Efficacy Population
E, P	Table 14.2.3.1	Survival Analysis for Overall Survival (OS)	Efficacy Population

Interim Analysis Flag	Output Type and Number	Output Title	Output Population
E, P	Table 14.2.3.2	Survival Analysis for Disease-Free Survival (DFS)	Primary Efficacy Population
E, P	Table 14.2.3.3	Survival Analysis for Event-Free Survival (EFS)	Efficacy Population
E, P	Table 14.2.3.4	Survival Analysis for Overall Survival (OS)	Efficacy Population
E, P	Table 14.2.3.5	Survival Analysis for Disease-Free Survival (DFS) by Major Pathologic Responder (MPR)	Primary Efficacy Population
E, P	Table 14.2.3.6	Survival Analysis for Event-Free Survival (EFS) by Major Pathologic Responder (MPR)	Efficacy Population
E, P	Table 14.2.3.7	Survival Analysis for Overall Survival (OS) by PD-L1 Group	Efficacy Population
E, P	Table 14.2.3.8	Survival Analysis for Disease-Free Survival (DFS) by PD-L1 Group	Primary Efficacy Population
E, P	Table 14.2.3.9	Survival Analysis for Event-Free Survival (EFS) by PD-L1 Group	Efficacy Population
S, E, P	Table 14.3.1.1.1	Overview of Adverse Events by Highest NCI CTCAE Grade, Neoadjuvant Atezolizumab Therapy Phase	Safety Population
	Table 14.3.1.1.2	Overview of Adverse Events by Highest NCI CTCAE Grade, Surveillance/Survival Follow-up Phase	Safety Population
S, E, P	Table 14.3.1.2.1	Adverse Events by Highest NCI CTCAE Grade, Neoadjuvant Atezolizumab Therapy Phase	Safety Population
	Table 14.3.1.2.2	Adverse Events by Highest NCI CTCAE Grade, Surveillance/Survival Follow-up Phase	Safety Population
S, E, P	Table 14.3.1.2a	Adverse Events by Highest NCI CTCAE Grade, Both Study Phases	Safety Population
S, E, P	Table 14.3.1.2b	Adverse Events With Onset Prior to Date of Surgery by Highest NCI CTCAE Grade, Neoadjuvant Atezolizumab Therapy Phase	Safety Population

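### The SAP runs exploratory DFS in a population that drops completely resected patients with unassessable MPR, although DFS needs no MPR score

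*SAP*

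**What the plan says.** SAP Section 6.3.3 makes three statements about who enters the DFS analysis.

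- Population: "Disease-free survival (DFS) will be analyzed in primary efficacy population".
- Restriction, in the same paragraph: "DFS will be analyzed only for patients who underwent surgery with complete resection".
- Kaplan-Meier paragraph, further down: "The overall survival, disease-free survival and event-free survival will be analyzed using the Kaplan-Meier method for the efficacy population".

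SAP Section 5 defines the two populations. The efficacy population is "all enrolled patients who have received at least one dose of the study drug and who do not have EGFR or ALK mutant tumors"; surgery is not required. The primary efficacy population narrows this by "excluding patients who have not received surgery after neoadjuvant treatment with Atezolizumab, and excluding subjects who have not had a complete resection", and then adds that "if major pathological response is unable to be assessed, then it will remain undetermined and the subject will be removed from this population".

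In SAP Section 7, Table 3 labels all six DFS outputs with the primary efficacy population: Tables 14.2.3.2 (overall), 14.2.3.5 (by MPR) and 14.2.3.8 (by PD-L1), and Figures 1.2.2, 1.2.5 and 1.2.8.

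Protocol Section 6.4.3 says "DFS will be analyzed only for patients who underwent surgery", with no condition on completeness of resection or on an MPR score. It also names the efficacy population for the Kaplan-Meier analysis of OS and DFS. SAP Section 6.6 declares no departure from the protocol.

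**The concern.** The rule that removes patients with undetermined MPR belongs to the primary analysis, where the missing item is the outcome itself. Carried over to DFS, it removes patients whose outcome is known. DFS starts at surgery with complete resection, ends at recurrence or death, and is censored at the last disease assessment. None of these needs a pathology score.

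Two things are at stake. One is the loss of valid follow-up data from the overall and PD-L1 DFS analyses. The other is a DFS estimate conditioned on whether a specimen could be scored. If that is associated with prognosis, the estimate shifts. The wording also gives a programmer conflicting instructions, because the population sentence, the restriction sentence and the Kaplan-Meier sentence do not describe the same set.

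**Working it through.** There is no stated DFS sample size, event count or power to reproduce. The check is a comparison of sets, followed by an illustration of scale.

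**Sets.** The definitions are nested, each contained in the one before:

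1. Efficacy population (SAP 6.3.3, Kaplan-Meier sentence; also named in Protocol 6.4.3).
2. Operated patients (Protocol 6.4.3, restriction).
3. Completely resected patients (SAP 6.3.3, restriction).
4. Completely resected patients with assessable MPR, which is the primary efficacy population (SAP 6.3.3, population sentence; SAP Table 3).

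Set 1 cannot be used literally, because a patient without surgery has no DFS start date and the restriction sentence excludes anyone without complete resection. Within the SAP this leaves sets 3 and 4. They differ by exactly the completely resected patients whose MPR is unassessable.

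**How many.** The documents give no complete-resection rate and no unscorable rate. Assume an efficacy population of 162 to 180 (180 is the planned enrollment), complete resection in 80% to 90%, and 1% to 5% of those unscorable.

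- Completely resected: 162 × 0.80 ≈ 130, up to 180 × 0.90 = 162.
- Dropped from DFS: about 1 (144 resected, 1% unscorable) to about 8 (162 resected, 5% unscorable).

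**Effect on the estimate.** Let N be the number of complete resections, D the DFS proportion among all of them, u the number unscorable and d the DFS proportion in those. Ignoring censoring, the value reported after exclusion is

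(D × N − d × u) / (N − u).

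Assume N = 140 and D = 0.70, so D × N = 98.

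| u | d | Calculation | Reported DFS | Shift (points) |
|---|---|---|---|---|
| 7 (5%) | 0.30 | (98 − 2.1) / 133 | 72.1% | +2.1 |
| 7 (5%) | 1.00 | (98 − 7) / 133 | 68.4% | −1.6 |
| 2 | 0.30 | (98 − 0.6) / 138 | 70.6% | +0.6 |
| 14 (10%) | 0.30 | (98 − 4.2) / 126 | 74.4% | +4.4 |

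If d = D, the shift is zero and only precision is lost.

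**Scale.** The 95% confidence half-width at N = 140 and D = 0.70, ignoring censoring, is 1.96 × √(0.70 × 0.30 / 140) = 1.96 × 0.0387 ≈ 7.6 points. Every shift in the table is smaller than this.

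**The case against.** A reader might infer that three incompatible DFS denominators are in force and that one of them brings in unresected patients. The documents do not support this. The restriction sentence in SAP 6.3.3 governs DFS, and the later sentence is best read as naming a parent population for three endpoints at once. Protocol 6.4.3 follows the same pattern, naming the efficacy population for Kaplan-Meier while separately limiting DFS to operated patients. All six DFS outputs carry a single label.

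A reader might also infer that the complete-resection condition contradicts the protocol in substance. That is too strong. Protocol Section 3.1.2 has patients without complete resection discontinued and replaced, and Protocol 6.4.3 starts DFS at the first disease-free date. The condition is a reasonable reading of the protocol, though narrower than its literal wording and not disclosed in SAP 6.6.

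The other side has further fair points. DFS is exploratory, in a single-arm study. The affected patients remain in OS and EFS, which use the efficacy population, and in Listing 16.2.6.14. Using one set for DFS overall and by MPR makes the MPR subgroups add up to the overall denominator.

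These points limit the consequence but leave the defect in place. Table 3 does not resolve it, since its consistent label is the one that excludes unscored patients. Additivity does not require dropping them, because a count of patients not evaluable for MPR reconciles the totals.

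**Conclusion.** The point holds in a narrow form. As written, the SAP discards observed DFS data from completely resected patients for lack of a score that DFS does not use, and this conflicts with its own restriction sentence. The Kaplan-Meier sentence needs correcting but does not widen the dispute beyond those patients.

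It would be tempting to conclude that DFS is biased. The documents do not show that: they give no unscorable rate and nothing on the prognosis of unscorable patients, so neither the presence nor the direction of bias can be established. With 140 resections, 70% DFS and 5% unscorable, all assumed, the shift is about −1.6 to +2.1 points when DFS in the unscorable patients lies between 100% and 30%. That is within sampling error. The primary MPR test, the futility rule, OS and EFS are untouched. The change is worth making because the exclusion serves no purpose for overall DFS or DFS by PD-L1 and is easily avoided.

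**What to change.** - In SAP 6.3.3, define the DFS set as efficacy-population patients with surgery and complete resection, whether or not MPR was evaluable.
- Amend the DFS clause of the Kaplan-Meier paragraph in SAP 6.3.3 to refer to that set.
- Relabel the population for Tables 14.2.3.2 and 14.2.3.8 and Figures 1.2.2 and 1.2.8 accordingly.
- Keep the MPR-evaluable subset only for DFS by MPR status (Table 14.2.3.5, Figure 1.2.5), and report there the number not evaluable.
- In SAP 6.6, state that the SAP limits DFS to complete resection, whereas Protocol 6.4.3 refers to patients who had surgery.

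The cost is wording and one population flag, with no new data. One small downside is that the MPR subgroups no longer sum to the overall DFS denominator; the not-evaluable count accounts for the difference.
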